Our central hypothesis is that our LIFT (+/- REAP) intervention will 1) improve adherence to recommended levels of exercise in end-stage liver disease 2) reduce pre-transplant frailty and 3) will improve pre- and post-transplant clinical outcomes.

STUDY ENDPOINTS:

Primary endpoints:

- Frailty (measured by Liver frailty index [LFI])
- Clinical outcomes: placement on LT waitlist, waitlist-mortality, post-transplant mortality, post-transplant disposition (acute rehabilitation, subacute rehabilitation center, home, etc), number of hospitalizations, duration of hospitalizations, liver related complications (ascites, hepatic encephalopathy, variceal bleeding, hepatorenal syndrome, hepatopulmonary syndrome, infections).
- Feasibility (measured by 8-question emailed survey)

[figure not shown]
Secondary endpoints:

- Endurance (measured by the 4-meter walk test).
- Patient adherence to the home exercise prescription (measured by daily diary counts of adherence to prescribed exercises, tracked on the TrueCoach application)
- Degree of hepatic encephalopathy (measured by List Sort Working Memory [LSWM] test and the Flanker Inhibitory Control and Attention [FICA])
- Patient-reported quality of life (measured by various PROMIS questionnaires)
- Feasibility/acceptability (measured by a study-specific questionnaire evaluating the acceptability and feasibility as reported by patients, providers and support staff)

STUDY INTERVENTION(S) / INVESTIGATIONAL AGENT(S):

Home exercise prescription (HEP) detailed below in study design.

PROCEDURES INVOLVED:

Recruitment for Quality of Life Assessment Study:

- A Northwestern Medicine Enterprise Data Warehouse (NMEDW) search will be used to identify all patients who have been seen in Transplant Evaluation Clinic and are currently being considered for liver transplantation or are already on the waitlist or have received a transplant.
- Alternatively, a list of the patients described above will be obtained from the transplant coordinator.

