- Baseline clinical data will be collected at time of enrollment via the NMEDW and via chart review (will submit EDW exception). Data will include: Age, gender, race, ethnicity, body mass index (BMI), employment status, education, marital status, etiology of liver disease, complications of liver disease (ascites, hepatic encephalopathy, presence of esophageal/gastric varices, history of variceal bleeding, hepatorenal syndrome, hepatopulmonary syndrome), medical history (coronary artery disease, chronic kidney disease, dialysis dependence, hypertension, hyperlipidemia), and baseline laboratory data (platelets, serum sodium, serum creatinine, PT/INR, total bilirubin, albumin, calculated MELD) (Appendix A, B)
- Components of baseline session: (1) personality assessment (2) patient-reported quality of life assessment (3) hepatic encephalopathy assessment (4) frailty assessment, (5) physical therapy introduction.

- Personality assessment
 - Setting:
 - If consented over the phone prior to clinic visit, the personality survey will be emailed/texted to patients and completed over the telephone with a team member.
 - If consented in clinic visit or while admitted inpatient, the personality survey will be completed in clinic or at bedside with a team member.
 - Tool: Modified Midlife Development Inventory (MIDI) Personality Scale
 - Time: 38 questions, 3-5 minutes
 - Data collected via REDcap
 - Appendix C
- Patient-reported quality of life assessment (in clinic)
 - Setting:
 - If consented over the phone prior to clinic visit, the QOL survey will be emailed/texted to patients and completed over the telephone with a team member.
 - If consented in clinic visit or while admitted inpatient, the QOL survey will be completed in clinic or at bedside with a team member.
 - Tools: PROMIS surveys: Physical function – Short form 8c, Cognitive Function
 - Time: ~15 questions, 5 minutes
 - Data collected via REDcap
 - Appendix D
- Hepatic encephalopathy assessment
 - Setting: in clinic or at bedside if inpatient.
 - Tools: List Sort Working Memory (LSWM) test, the Flanker Inhibitory Control and Attention (FICA) test, Pattern Comparison Processing Speed Test administered on ipad and keyboard.
 - Time: 16 minutes (LSWM – 7 minutes, FICA – 3 minutes, PCPS – 3 minutes)
 - Appendix E
- Frailty assessment
 - Setting: in clinic or at bedside if inpatient.
 - Tools: Liver Frailty Index, 4-meter walk test
 - Balance testing
 - Repeat chair stands
 - Grip testing

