 - This is performed in all patients in clinic, regardless of whether they consent for this study specifically.
 - Time: 5 minutes
 - Appendix F
- Physical therapy introduction
 - Setting: in clinic or at bedside if inpatient.
 - Provide equipment (weights, therabands, dynamometer, Truecoach smart phone application if not installed over the phone after consent was received)

- Demonstrate initial home exercise prescription, which will include a set of exercises to be done at home on a daily basis (cardio exercises, resistance exercises). These recommended exercises will be within standard of care.
- Time: 10-15 minutes

LIFT subgroup:

Follow up:

- *Text reminders (every day):*
 - An automated system will be used to generate and send daily text messages reminding patients to follow their HEP. Texts will be standardized and not contain any PHI.
- *Exercise data collection (continuously):*
 - Data continuously collected via TrueCoach smart phone application to document adherence to exercise regimen. If patients are unable to appropriately track adherence on the smart phone application, this data will be collected at weekly videoconference/telephone check-ins detailed below.
- *LFI calculation at home (every 4 weeks)*
 - A dynamometer will be given to each patient at time of enrollment. A video will be uploaded on the TrueCoach application demonstrating how to perform grip strength testing.
 - Balance testing and chair stands will be tested at home.
 - A team member will walk patients through each test via a videoconference call.
- *Patient-reported quality of life assessment at home (every 4 weeks, surveys emailed - Patients will be called by a team member who will walk the patient through the survey and record data over the phone)*
 - Tools: PROMIS surveys: Physical function – Short form 8c, Cognitive Function
 - Data collected via REDcap
- *Personality assessment at home (every 4 weeks, survey emailed - Patients will be called by a team member who will walk the patient through the survey and record data over the phone)*
 - Tool: Modified Midlife Development Inventory (MIDI) Personality Scale
 - Data collected via REDcap
- *Videoconference/telephone check-in (every 1 week):*
 - Performed by a member of the research team.
 - If patients are unable to track adherence to exercise regimen via TrueCoach application, the team member will document daily physical activity on this call.

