 - If patients have questions regarding exercise regimen, they will be contacted by a physical therapist.
 - Progress reviewed and exercise regimen potentially adjusted by a physical therapist based on data collected and patient experience.
- *Clinical data collection via NEDW and review of EMR (every 4 weeks)*
 - Number of hospitalizations, intensive care unit admissions, duration of hospitalizations, development of decompensating events (ascites, hepatic

encephalopathy, variceal bleeding), transplant status, type of LT (living donor LT, simultaneous liver-kidney), duration of hospital admission for LT, duration of ICU admission for LT, duration of intubation post-LT, post-transplant discharge disposition, date of death, cause of death, post-transplant complications (rejection, infection, biliary complications).

- *Clinic visits (every 3 months, same tools as noted above)*
 - Patient-reported quality of life assessment
 - Hepatic encephalopathy assessment
 - Frailty assessment, 4-meter walk test (standard of care)
 - Physical therapy in person update (standard of care)
 - Data collection via NMEDW extraction and chart review: Number of hospitalizations, intensive care unit admissions, duration of hospitalizations, development of decompensating events (ascites, hepatic encephalopathy, variceal bleeding), transplant status, type of LT (living donor LT, simultaneous liver-kidney), duration of hospital admission for LT, duration of ICU admission for LT, duration of intubation post-LT, post-transplant discharge disposition, date of death, cause of death, post-transplant complications (rejection, infection, biliary complications).
- Feasibility assessment (for those who remain in the study for at least 1 month or until receiving a liver transplant; surveys emailed)
 - Tool: 8 -question survey emailed to eligible subjects as noted above.
 - Data collected via REDCap.
 - Time: < 3 minutes
 - Appendix G

All participants who enroll for the PT intervention will be randomized (1:1) into the LIFT subgroup or the LIFT + REAP subgroup at 2 weeks after enrollment/baseline session. The LIFT subgroup will continue to follow up as detailed above. The LIFT + REAP subgroup will undergo Realistic Effort Action Planning (REAP), which is described below:

LIFT + REAP subgroup:

Follow up:

- *REAP introduction (2 weeks after enrollment, via telephone/videoconference, time: 30 minutes)*
 - Performed by a member of the research team.

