- Only the principal investigator and co-investigators listed on this study will have access to harvested patient data.
- Any documents containing identifiable information will be destroyed within five years of project completion using electronic "shredding" software.

POTENTIAL BENEFITS TO PARTICIPANTS

PT Intervention Study:

Improvement in physical function (decreased frailty), which should improve pre- and post-transplantation outcomes, is the primary benefit of participating in the study. Based on the current literature demonstrating the negative impact of frailty on clinical outcomes in liver transplantation, improvement in clinical outcomes with improvement in physical function is likely.

QOL Assessment Study:

There is no direct benefit to participation.

DATA MANAGEMENT AND CONFIDENTIALITY

Only IRB approved personnel will have access to the data. All data will be stored on FSM shared drive-accessed only by approved personnel. All data is accessed through password protected computer kept in locked offices. All patient identifiers will be stored in a separate password protected file.

These data will be presented at national meetings (i.e. American Transplant Congress, etc) and a manuscript will be written for consideration of publication in respected, peer-reviewed journals (i.e. American Journal of Transplantation). All publications will include only aggregated data and no patient identifiers will ever be reported. Data will be stored until 3 years after the end of the project and will be destroyed.

QOL Assessment study

As PHI will be collected under a waiver of written HIPAA authorization, the PHI collected for these participants will not be reused or disclosed to any other person or entity, and the identifiers will be destroyed at the time of IRB closure.

Statistical analysis:

Chi-squared tests will be used to assess differences in categorical clinical endpoints and T-tests will be used to assess differences in continuous clinical endpoints between the LIFT and LIFT + REAP subgroups. Multivariate analysis will be used to assess clinical factors associated with clinical endpoints in each group. Survival analysis will be conducted after controlling for all the variables that are significant during regression analysis.

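### The t-test planned for continuous endpoints does not adjust for the LFI measured before randomisation, and survival covariates are picked by significance: precision and pre-specification are lost, not validity

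*Combined protocol and SAP*

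**What the plan says.** The analysis plan is one short paragraph, Statistical analysis, under Data Management and Confidentiality, followed by a sentence on sample size.

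- **Continuous endpoints:** "T-tests will be used to assess differences in continuous clinical endpoints" between the two randomised subgroups. No covariate, time point or summary measure (follow-up value or change) is named.
- **Factors:** "Multivariate analysis will be used to assess clinical factors associated with clinical endpoints in each group".
- **Survival:** "Survival analysis will be conducted after controlling for all the variables that are significant during regression analysis". No threshold, candidate list or model is given.

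Study Endpoints lists "Frailty (measured by Liver frailty index [LFI)" first among the primary endpoints. The baseline session includes a frailty assessment, and of this assessment the protocol says "This is performed in all patients in clinic, regardless of whether they consent for this study specifically"; inpatients are assessed at the bedside. Participants are then "randomized (1:1) into the LIFT subgroup or the LIFT + REAP subgroup at 2 weeks after enrollment/baseline session". Follow-up in both subgroups includes "LFI calculation at home (every 4 weeks)" and a frailty assessment at the 3-monthly clinic visits.

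**The concern.** Baseline LFI is measured before allocation, so REAP cannot have affected it, and it is likely to be correlated with later LFI. A two-sample t-test on follow-up LFI leaves that explained variation in the error term and gives no protection against chance imbalance. A t-test on change uses the baseline value, but less efficiently than ANCOVA. Either way, a single comparison leaves most of the repeated measurements unused.

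Choosing survival covariates by significance makes the adjusted model depend on the data. A recognised prognostic factor may drop out by chance, and no reader can know in advance which model will be reported. The sentence on factors within each group names neither an arm term nor an interaction, so it gives no way to compare a factor between arms.

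**Working it through.** **The plan's own figure.** The sample size of 500 cannot be reproduced, because no alpha, power, effect size or standard deviation is stated. As a back-calculation only, assume 250 per arm and two-sided alpha 0.05. The detectable standardised difference is then d = (1.960 + 0.842) × √(2/250) = 0.251 at 80% power, and (1.960 + 1.282) × √(2/250) = 0.290 at 90%. That is the reason for using d = 0.25 below.

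**Inputs**

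- From the protocol: LFI is a primary endpoint, it is measured before randomisation, and allocation is 1:1.
- Assumed: d = 0.25, alpha 0.05 two-sided, baseline-follow-up correlation r, equal variances at baseline and follow-up, and arm size. The table under Participant Population(s) gives 500 for all groups, and the Quality of Life Assessment Study falls under the same protocol. The randomised arms may therefore be well below 250, so a range is shown.

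**Variance relative to a t-test on follow-up LFI**

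- t-test on follow-up: 1
- t-test on change: 2(1 − r)
- ANCOVA: 1 − r²
- ANCOVA relative to change: (1 − r²) / [2(1 − r)] = (1 + r)/2

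| r | Change | ANCOVA | ANCOVA ÷ change |
|---|---|---|---|
| 0.3 | 1.40 | 0.91 | 0.65 |
| 0.5 | 1.00 | 0.75 | 0.75 |
| 0.7 | 0.60 | 0.51 | 0.85 |
| 0.8 | 0.40 | 0.36 | 0.90 |

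To match 500 unadjusted patients, ANCOVA needs 500 × 0.75 = 375 at r = 0.5 and 500 × 0.51 = 255 at r = 0.7.

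**Power** = Φ(d√(n/(2v)) − 1.960), where n is the number per arm and v the variance factor above. For example, with n = 100 and v = 1: 0.25 × √50 = 1.768, and Φ(−0.192) = 42%. With v = 0.51: 1.768/√0.51 = 2.476, and Φ(0.516) = 70%.

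| Per arm | Follow-up t-test | Change t-test, r = 0.5 / 0.7 | ANCOVA, r = 0.5 / 0.7 |
|---|---|---|---|
| 100 | 42% | 42% / 63% | 53% / 70% |
| 125 | 51% | 51% / 72% | 63% / 79% |
| 250 | 80% | 80% / 95% | 90% / 97.5% |

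**Type I error.** In a simulation with no treatment effect (4,000 runs per setting, 125 and 250 per arm, r = 0.5 and 0.7), the rejection rate was between 4.3% and 5.7% for all three analyses. The choice affects precision, not validity.

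**Screening.** The baseline session lists 27 clinical and laboratory variables. If all were unrelated to outcome, independent, and tested at an assumed 0.05, the chance of selecting at least one would be 1 − 0.95²⁷ = 75%. This shows how far chance can shape the covariate set. It does not measure bias in the treatment effect.

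**The case against.** **The t-test may not be meant for LFI.** The sentence concerns continuous clinical endpoints, and Study Endpoints lists frailty apart from clinical outcomes. That is fair: applying it to LFI is an inference. If it does not apply, however, a primary endpoint has no stated between-arm analysis.

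**The baseline may be used after all.** The plan does not say whether follow-up or change is tested. One therefore cannot say that the plan ignores baseline LFI, only that it does not adjust for it. Against a change-score test the gain is smaller: 63% to 70% at r = 0.7 with 100 per arm, and 95% to 97.5% with 250.

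**This is a pilot, and an unadjusted t-test is valid under randomisation.** Both stand. They limit the point to efficiency and pre-specification.

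A reader might infer more than the text supports:

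- *That repeated LFI values will be pooled as if independent, inflating false positives.* The plan is silent on the repeats and does not propose this.
- *That the survival model will adjust for post-randomisation events such as hospitalisation or decompensation and so hide a real effect.* The plan does not restrict candidates to baseline variables, but silence is not a plan to include later events.
- *That significance in one arm and not the other will be read as a difference.* The sentence on each group is loosely worded and concerns factors, not the treatment effect. No such comparison is announced.
- *That screening will bias a comparison of LIFT with the retrospective controls.* The paragraph names only LIFT against LIFT + REAP. The missing analysis for the controls is a separate matter.

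**Conclusion.** The point holds as one of efficiency and pre-specification. The plan leaves out an adjustment that is available for the randomised comparison from data it already collects. On the follow-up t-test reading, the variance that ANCOVA would remove is 25% to 49% for r between 0.5 and 0.7 (9% at r = 0.3, 64% at r = 0.8). On the change-score reading it is 25% to 15% for the same r of 0.5 to 0.7. The correlation, effect size, alpha and arm sizes are all assumptions. The further gain from modelling the repeats is not quantified here.

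The survival sentence should be changed because its covariate set cannot be known in advance. No size of bias is claimed for it: randomisation protects the comparison between LIFT and LIFT + REAP from confounding in expectation. The change should be made before outcome data are examined, but nothing here makes the planned randomised comparison invalid.

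**What to change.** 1. For LIFT against LIFT + REAP, replace the t-test for LFI with ANCOVA at one named time point, or with a mixed model for repeated measures (arm, visit, arm-by-visit), with baseline LFI as covariate. Do the same for the other continuous endpoints measured at baseline: 4-metre walk, PROMIS, LSWM and FICA. State how LFI after transplant or death is handled, since neither model settles that by itself.
2. Replace the significance rule in the survival sentence with a short named set of baseline-only covariates, for example baseline LFI, MELD and age.
3. Where factors are compared between arms, fit one model to both arms with an arm term and arm-by-factor interactions.

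For the randomised comparison the cost is wording: these baseline measures are already in the baseline session, and no visit or procedure is added. This does not carry over to the retrospective controls. Their baseline data list contains no LFI. LFI scores appear only among their follow-up data, limited to what is already in the medical record, so any adjusted analysis using them needs its own covariate set and a check of availability.
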